11.1. Study Design/Endpoints

Primary Endpoint

Change in anxiety will be assessed by the Visual Analog Mood Scale (VAMs) anxiety subscale, ascertained on the day of the drug administration pre-dose (T1) and 3(+/- 1) hour after drug administration (T2). The change in anxiety score will be calculated for each patient and a Wilcoxon rank sum test will be used to assess whether the change score is different among patients randomized to CBD as compared to placebo.

Secondary and Exploratory Endpoints

Secondary and exploratory objectives include a description of the side-effect profile of CBD in oncology patients, patient reported experience and acceptability of CBD, and the estimation of the change in state anxiety as well as other VAMs subscales (Afraid, Confused, Sad, Angry, Energetic, Tired, Happy, and Tense). Secondary endpoint analyses will be considered exploratory (no alpha adjustment given the relatively small sample size) and will provide context for interpretation of the primary endpoint.

Randomization

Patients will be randomized 2:1 to CBD or placebo using permuted blocks within strata (one single stratification variable, baseline anxiety with 2 levels, will be used) and a double-blind procedure will be followed. Randomization will be completed by the Office of Data Quality (ODQ). ODQ will send the randomization assignment to the DFCI Research Pharmacy and the pharmacy will dispense the medication. The justification for the 2:1 randomization is to better assess side-effects and to allow for more qualitative data at the completion of the study.

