5.1.3 Instruments measuring study outcomes:

Demographic questionnaire (Baseline):

Variables of interest will be obtained via self-report and include: age, ethnicity, race, marital status, education, and occupational status.

Cannabis History Questionnaire (Baseline):

Cannabis use history will be obtained via self-report.

Generalized Anxiety Disorder- 7 (GAD-7) (Baseline, Timepoint 1): The widely used and validated GAD-7 measures anxiety severity on a 4-point Likert-type scale from not at all to

nearly every day. The presence of baseline anxiety, as measure by a GAD-7 score >4 , is necessary for inclusion in this study.

Patient Health Questionnaire (PHQ-9) (Baseline, Timepoint 1): The widely used and validated PHQ-9 is a 9-item depression severity measure, with scores ranging from 0 to 27. Patients are asked to rate how they felt over the past two weeks using a 4-point Likert scale. Given that anxiety and depression are closely intertwined, this measure will help us to demonstrate that the active drug and placebo arms manifest similar levels of dysphoric distress. This measure will also help in screening to rule out “uncontrolled mental illness.”

VAMS (Timepoint 1, and Timepoint 2): The Visual Analog Mood Scale (VAMS) a validated in-the-moment measure of eight specific mood states: Afraid, Confused, Sad, Angry, Energetic, Tired, Happy, and Tense. Each scale consists of a 100 mm vertical line connecting a neutral face and a face displaying a particular mood state (with an accompanying descriptor). Subjects are asked to mark their mood along this continuum. The measure is scored using a metric ruler and the “Afraid” subscale will serve as our primary endpoint. Other subscales will serve as exploratory endpoints.

EORTC-QLQc30-nausea (Timepoint 1, and Timepoint 2): The EORTC-QLQc30-nausea is a widely used and validated measure of symptom burden. It consists of 30-items, the first 28 of which employ a four-point scale (the final two are measured along a seven-point scale). Single item measures range in score from 0 to 100, with higher scores representing lower symptom burden. For the purposes of this study we will administer two items from the EORTC-QLQc30 on nausea and vomiting to assess a secondary endpoint.

Numeric Pain Rating Scale (Baseline, Timepoint 1, Timepoint 2): This widely used in-the-moment pain intensity scale is scored from 0 to 10 (with 10 representing “worst possible” pain). The NPRS will again help us to assess secondary endpoints.

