11. STATISTICAL CONSIDERATIONS

This is a phase II, randomized, placebo-controlled study to assess the preliminary efficacy of offering a single dose of CBD versus placebo in reduction of anxiety in patients with advanced (stage IV) solid tumor anticipating CT to assess tumor burden. Eligible patients must have measurable anxiety-- at least “mild” anxiety as measured by the GAD-- at the pre-screen visit.

Anxiety level at each of the time points (pre-screening visit, pre-dose, and 3[+/-1] hour post dose) will be plotted for each study group. The paired change (pre-dose to post-dose) in anxiety will be estimated along with a 95% confidence interval for each study group. The change in anxiety will be compared by study group with a Wilcoxon rank sum test. The side-effect profile, as measured by the PRO-CTCAE will be tabled according to side effect. Patient reported experience with CBD and the acceptability will be summarized with descriptive statistics and qualitative methodology as appropriate

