11.2. Sample Size, Accrual Rate and Study Duration

Accrual Targets				
Ethnic Category	Sex/Gender			
	Females		Males	Total
Hispanic or Latino	8	+	0	= 8
Not Hispanic or Latino	192	+	0	= 192
Ethnic Category: Total of all subjects	200	(A1)	+	0 (B1) = 200(C1)
Racial Category				
American Indian or Alaskan Native	0	+	0	= 0
Asian	4	+	0	= 4
Black or African American	4	+	0	= 4
Native Hawaiian or other Pacific Islander	0	+	0	= 0
White	192	+	0	= 192
Racial Category: Total of all subjects	200	(A2)	+	0 (B2) = 200(C2)
	(A1 = A2)		(B1 = B2)	(C1 = C2)

The Visual Analog Mood Scale (VAMs) anxiety subscale is measured on a 0 to 100 scale and is then converted to a T-score standardized by age and gender. The VAMs manual suggests that, in a pre-test/post-test setting, a score differing by 20T indicates a reliable change in mood and a score differing by 30T indicates a reliable and clinically meaningful change in mood²⁰. Studies comparing depressed and non-depressed psychiatric patients indicated possible standard deviations ranging from 15-36²⁰. Additionally, a previous study¹⁸ demonstrated that the change from pre-dose to 140 minutes post-dose in the VAMs anxiety subscale was approximately 16.7 for CBD and 3.5 for placebo respectively in 10 subjects with social anxiety disorder. In the same sample, the reported standard deviations pre- and post- CBD ranged from approximately 7 to 15.

A two-sided, Wilcoxon rank sum test will be used to assess the difference in change in anxiety score between CBD and placebo. Estimating a minimal change in anxiety for patients assigned to placebo, a difference in the change score of 20 is to be targeted. Assuming a two-sided significance level of 0.05, a 2 to 1 randomization, and a standard deviation of 20, there is 80% power to detect a difference of 20 (effect size = 1) in the change in anxiety score between CBD and placebo with 45 patients (30 CBD, 15 placebo). Based on an approximated 10% attrition rate, 50 patients will be enrolled and randomized.

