11.3. Stratification Factors

Randomization will be stratified on baseline anxiety level, mild to moderate (5-14) versus severe (15-21).

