11.5. Analysis of Primary Endpoints

Please see above.

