11.7.2. Evaluation of the Primary Efficacy Endpoint

Sub-analyses may then be performed on the basis of a subset of participants, excluding those for whom major protocol deviations have been identified (e.g., early death due to other reasons, early discontinuation of treatment, major protocol violations, etc.). However, these sub-analyses will not serve as the basis for drawing conclusions concerning treatment efficacy, and the reasons for excluding participants from the analysis will be clearly reported. If applicable to the endpoint, the 95% confidence intervals will also be provided.

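### The primary Wilcoxon test is valid and adequately powered at the plan's SD, but the plan names no between-arm estimate with a CI and leaves T1 VAMS Afraid and the GAD-7 stratum out of the analysis

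*Combined protocol and SAP*

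**What the plan says.** The between-arm analysis of the primary endpoint is a rank test on the change from pre-dose (T1) to 3 (+/-1) hours post-dose (T2). Section 11.1 states that "a Wilcoxon rank sum test will be used to assess whether the change score is different among patients randomized to CBD as compared to placebo", and Section 11.2 repeats it: "A two-sided, Wilcoxon rank sum test will be used to assess the difference in change in anxiety score between CBD and placebo". Section 11.5, which is headed as the primary analysis, contains only "Please see above".

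Estimation appears in two places. The opening of Section 11 says: "The paired change (pre-dose to post-dose) in anxiety will be estimated along with a 95% confidence interval for each study group". Section 11.7.2, after text on sub-analyses that exclude protocol deviators, adds: "If applicable to the endpoint, the 95% confidence intervals will also be provided". The first is within-arm. The second is conditional and names no contrast or estimator.

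Randomisation is 2:1 in permuted blocks, stratified by baseline GAD-7, 5-14 versus 15-21 (Sections 4.1, 11.1 and 11.3). No analysis section uses the stratum. VAMS Afraid is collected at T1 and T2 (Sections 5.1.3 and 9), and T1 enters the analysis only by subtraction.

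The naming of the endpoint is not uniform. The primary objective, Section 5.1.3 and the study calendar make Afraid primary. Section 11.1 calls the primary measure the anxiety subscale and lists Afraid among the secondary subscales.

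**The concern.** The stated aim is preliminary efficacy against placebo. What a follow-on trial needs from this one is the size of the CBD-placebo difference and its precision. As written, the plan delivers a p-value and two separate within-arm intervals, and the reader has to construct the difference.

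With about 30 and 15 patients, the arms can also differ by chance at T1. A change score removes the T1 difference with a fixed slope of 1. If the true slope of T2 on T1 is below 1, part of a chance imbalance stays in the estimated effect and some precision is given up. An analysis that follows the design would also carry the factor used to stratify randomisation.

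**Working it through.** **Inputs from Section 11.2.** The plan's power statement begins "Assuming a two-sided significance level of 0.05, a 2 to 1 randomization, and a standard deviation of 20". The target difference is 20, stated power 80%, 45 evaluable (30 CBD, 15 placebo), attrition 10%, 50 enrolled.

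**1. The plan's own figure.**
- Noether's formula: P(X>Y) = Φ(1/√2) = 0.760 and allocation fraction c = 1/3, so N = (1.960 + 0.842)² / [12 × (1/3) × (2/3) × 0.260²] = 43.5. That is 45 at exact 2:1, where power is 81.4%.
- Noncentral t with the minimum relative efficiency of 0.864: the smallest 2:1 total is 45, with power 81.6%.
- Simulated exact Wilcoxon test on normal data: power 85.3%, type I error 4.7%.
- Attrition: 45 / 0.9 = 50.

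The stated 80% reproduces. When randomisation is simulated in stratified blocks and the stratum is ignored in the test, type I error is about 4.1% to 4.7%, so the unstratified test is valid and at most slightly conservative.

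**2. Precision of the between-arm difference, unadjusted.**
- Mean difference: t(43) × 20 × √(1/30 + 1/15) = 2.017 × 6.325 = 12.75 points half-width.
- Hodges-Lehmann shift (simulated, normal data): about 13.3 points.

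**3. Adjusting for T1.** The documents give no pre-post correlation r, so it is an assumption here, shown over a range. With equal T1 and T2 variances s², the change-score variance is 2s²(1 − r) = 400. The variance of T2 given T1 is s²(1 − r²) = 400 × (1 + r)/2, so the residual SD is 20√((1 + r)/2). The half-width by formula is t(41) × residual SD × √0.1, with t(41) = 2.020. The simulated half-widths are about 0.2 larger.

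| r (assumed) | 0.3 | 0.5 | 0.7 | 0.85 |
|---|---|---|---|---|
| ANCOVA residual SD | 16.1 | 17.3 | 18.4 | 19.2 |
| CI half-width, formula | 10.3 | 11.1 | 11.8 | 12.3 |
| CI half-width, simulated | 10.5 | 11.3 | 12.0 | 12.5 |
| ANCOVA power at 20, simulated | 96% | 93% | 90% | 88% |
| Wilcoxon power at 20, simulated | about 85% | about 85% | about 85% | about 85% |

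About 2 points of the power gain come from moving to a parametric test (noncentral t on change: 87.1%, against 85.3%), not from the covariate.

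**4. Chance T1 imbalance.** A 1-SD imbalance between arms is s√0.1, and it moves the change-score difference by (1 − r) times that, which equals 6.325 × √((1 − r)/2). This gives 3.7, 3.2, 2.4 and 1.7 points at the four values of r. These are modest against a target of 20.

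**5. Sensitivity to normality.** With heavy-tailed residuals (t with 3 df, assumed) and the same r values, simulated power is 93 / 94 / 96 / 97% for the Wilcoxon test and 95 / 94 / 91 / 90% for ANCOVA. The advantage is gone at r of about 0.5 and reversed above it.

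**The case against.** The best defence is that nothing is lost. The arms are independent, so if the per-arm estimates are means, the difference and its interval follow from them. Half-widths of 7.47 and 11.08 give standard errors of 7.47/2.045 = 3.65 and 11.08/2.145 = 5.16. These combine to 6.32, hence 2.017 × 6.32 = 12.75, the same as in step 2. This stands: a reader may infer that the effect size cannot be recovered from the planned output, and that goes too far. The gap is an unspecified line of reporting. It is still worth closing, because the estimator that matches a rank test is not recoverable from two intervals, and Section 11.7.2 commits to no contrast.

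It is also fair to say that a rank test is a reasonable choice with 15 placebo patients on a bounded 100 mm scale, and that any ANCOVA gain depends on an unknown r. That stands too, and is why the ANCOVA is proposed only as supportive.

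Three stronger readings are tempting, and the documents do not support them.
- That power fails across the SDs of 15-36 cited in Section 11.2. The section does not say that these are change-score SDs. It also cites pre and post SDs of about 7 to 15 from the CBD study, which with equal variances and r of at least 0 imply a change SD of at most √2 × 7 = 9.9 to √2 × 15 = 21.2.
- That the cited SDs bound r. With change SD 20, r = 1 − 400/(2 × SD²) gives 0.11 at 15 and 0.85 at 36, but −3.1 at 7, which is impossible. The bound depends on which cited source is chosen.
- That the plan misleads because the within-arm intervals may overlap when the arms differ. The plan compares arms by the Wilcoxon test and never infers from overlap.

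**Conclusion.** The point holds as a low-cost improvement. The planned test is valid and meets its stated power at a change SD of 20. What is absent is a named between-arm estimate with a CI, a covariate role for T1 VAMS Afraid, and any analysis by the GAD-7 stratum.

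The missing estimate does not depend on any assumption. The benefit of T1 adjustment does. Under normality, equal variances, change SD 20 and r of 0.3 to 0.85, power is about 3 to 11 points higher than for the Wilcoxon test, and the interval is about 2% to 18% narrower than for the unadjusted mean difference (12.5/12.75 and 10.5/12.75). With heavy tails the power gain can reverse. No power gain is claimed for the stratum. The reason to include it is consistency with the randomisation, and leaving it out does not invalidate the test.

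**What to change.** Amend Sections 11, 11.1 and 11.5 before unblinding:

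1. Keep the two-sided Wilcoxon rank sum test on T1-to-T2 change as the primary analysis, stratified by GAD-7 level 5-14 / 15-21 (van Elteren).
2. Report the between-arm Hodges-Lehmann shift in VAMS Afraid change with its 95% CI.
3. Prespecify one supportive ANCOVA of T2 VAMS Afraid on arm, T1 VAMS Afraid and GAD-7 stratum, with the adjusted difference and 95% CI. Use the same metric (raw or T-score) at both times.
4. In Section 11.5, replace the cross-reference with this text.
5. In the same edit, reconcile the anxiety-subscale wording of Section 11.1 with the primary objective, Section 5.1.3 and the calendar, which name Afraid.

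The cost is wording and a little more analysis. T1 VAMS Afraid and baseline GAD-7 are already collected, and no patients or visits are added. Stratifying the rank test may give up a little power if the stratum is not prognostic. The ANCOVA gain shrinks as r rises and can reverse with heavy tails, so it should not replace the primary test.

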11.2. Sample Size, Accrual Rate and Study Duration

Accrual Targets				
Ethnic Category	Sex/Gender			
	Females		Males	Total
Hispanic or Latino	8	+	0	= 8
Not Hispanic or Latino	192	+	0	= 192
Ethnic Category: Total of all subjects	200	(A1)	+	0 (B1) = 200(C1)
Racial Category				
American Indian or Alaskan Native	0	+	0	= 0
Asian	4	+	0	= 4
Black or African American	4	+	0	= 4
Native Hawaiian or other Pacific Islander	0	+	0	= 0
White	192	+	0	= 192
Racial Category: Total of all subjects	200	(A2)	+	0 (B2) = 200(C2)
	(A1 = A2)		(B1 = B2)	(C1 = C2)

The Visual Analog Mood Scale (VAMs) anxiety subscale is measured on a 0 to 100 scale and is then converted to a T-score standardized by age and gender. The VAMs manual suggests that, in a pre-test/post-test setting, a score differing by 20T indicates a reliable change in mood and a score differing by 30T indicates a reliable and clinically meaningful change in mood²⁰. Studies comparing depressed and non-depressed psychiatric patients indicated possible standard deviations ranging from 15-36²⁰. Additionally, a previous study¹⁸ demonstrated that the change from pre-dose to 140 minutes post-dose in the VAMs anxiety subscale was approximately 16.7 for CBD and 3.5 for placebo respectively in 10 subjects with social anxiety disorder. In the same sample, the reported standard deviations pre- and post- CBD ranged from approximately 7 to 15.

A two-sided, Wilcoxon rank sum test will be used to assess the difference in change in anxiety score between CBD and placebo. Estimating a minimal change in anxiety for patients assigned to placebo, a difference in the change score of 20 is to be targeted. Assuming a two-sided significance level of 0.05, a 2 to 1 randomization, and a standard deviation of 20, there is 80% power to detect a difference of 20 (effect size = 1) in the change in anxiety score between CBD and placebo with 45 patients (30 CBD, 15 placebo). Based on an approximated 10% attrition rate, 50 patients will be enrolled and randomized.

11.3. Stratification Factors

Randomization will be stratified on baseline anxiety level, mild to moderate (5-14) versus severe (15-21).

11.4. Interim Monitoring Plan

N/A

11.5. Analysis of Primary Endpoints

Please see above.

11.6. Analysis of Secondary Endpoints

This will be an intent-to-treat analysis. Secondary endpoint analyses will be considered exploratory and will provide context for interpretation of the primary endpoint.

11.7. Reporting and Exclusions

11.7.1. Evaluation of Toxicity

All participants will be evaluable for toxicity from the time of their first treatment.

11.7.2. Evaluation of the Primary Efficacy Endpoint

Sub-analyses may then be performed on the basis of a subset of participants, excluding those for whom major protocol deviations have been identified (e.g., early death due to other reasons, early discontinuation of treatment, major protocol violations, etc.). However, these sub-analyses will not serve as the basis for drawing conclusions concerning treatment efficacy, and the reasons for excluding participants from the analysis will be clearly reported. If applicable to the endpoint, the 95% confidence intervals will also be provided.

